### List of abbreviations

ADR	Adverse Drug Reaction
AE	Adverse event
ALT/SGPT/ ALAT	Alanine Transaminase /Serum Glutamic Pyruvic Transaminase/ Alanine Aminotransferase
ANC	Absolute Neutrophil Count
AP	Alkaline Phosphatase
AST / SGOT/ASAT	Aspartate Transaminase/ Serum Glutamic Oxaloacetic Transaminase/Aspartate Aminotransferase
ART	Adverse Reaction Terminology
CRO	Contract Research Organization
CSR	Clinical Study Report
CRP	(C-Reactive Protein) Level
ECG	Electrocardiogram
EOS	End of Study
EoT	End of Trial
eCRF	Electronic case report form
FiO2	Fraction of Inspired Oxygen
i.v.	intravenous(ly)
IMP	Investigational Medical Product
IRC	Independent Review Committee
IE	In evaluable
MedDRA	Medical Dictionary for Regulatory Activities
PP	Per Protocol
PaO2	Partial Pressure of Oxygen
SAE	Serious Adverse Event
SAS	Statistical Analysis System
SAP	Statistical Analysis Plan
UNK	Unknown
US	Ultrasound
V	Visit
Wk	Week

## **1 Purpose**

The purpose of this statistical analysis plan (SAP) is to assess the efficacy and safety of Itolizumab administered in patients with COVID-19 complications in comparison with the Best of Care that will be included in the clinical study report. And this document is based on protocol version 5.0, 3rd June 2020. SAP will ensure that the data listings, summary tables and figures are complete; and the statistical methodologies used are appropriate to allow valid conclusions in line with the study's objectives. This document will be appended to the clinical study report (CSR). The statistical analyses will be performed in accordance with the ICH-E9 guidelines "Statistical Principles for Clinical Trials" and relevant guidelines from Central Drugs Standard Control organization (CDSCO). If circumstances arise during the study such that more appropriate analytic procedures become available, this statistical analysis plan (SAP) may be revised. Any revisions to the SAP (both alternative and additional methods) will be made prior to database lock and reasons for such revisions will be described in the final Clinical Study Report (CSR).

## **2 Responsibility**

Biocon Biologics India Limited/Designated CRO will be responsible for the conduct of statistical analyses, and the production and quality control of all tables, figures and listings).

## **3 Study Objectives**

Coronavirus disease 2019 (COVID-19) progresses to respiratory complications as consequence of the exaggerated immune response of the host, producing a pro-inflammatory cytokine storm syndrome (i.e.: IL-6, TNF) and cytopenia, with a high mortality rate. Emergency treatments aiming to reduce individual cytokines (IL-6 and IL-1) specifically [or indirectly (JAK inhibitors and CCR5 antagonists) have shown survival benefit in patients with hyperinflammation, without increased adverse events. However, not being sufficient to reduce the rising mortality by COVID-19 other interventions to immunomodulate the life-threatening hyperinflammation are urgently needed. Therefore, the proposal for use of an anti-CD6 monoclonal antibody (Itolizumab) for the treatment of the COVID-19 complications (cytokine storm syndrome).

### **3.1 Trial Objectives**

#### **3.1.1 Primary Objectives**

To study the efficacy and safety of adding Itolizumab in patients with Moderate to Severe COVID-19 complications (Cytokine Release Syndrome).

#### **3.1.2 Secondary Objectives**

To study the effect of immunomodulation by Itolizumab and its correlation to clinical improvement by evaluating biomarker data (IL6, TNF-a, IL17, IL1, Interferon -A etc.) before and after Itolizumab treatment

## 3.2 Outcome Measures

### 3.2.1 Primary endpoint

1. Proportion of patients with deterioration of lung function as measured by\*:
  - Stable SpO2 without increasing FiO2
  - Stable PaO2 without increasing FiO2
2. Reduction of endo-tracheal intubation rate, measured as rate of patients needing intubation\*
3. Reduction in proportion of patients who need\*
  - Non-invasive ventilation
  - Invasive mechanical ventilation
  - High flow nasal oxygen
4. Time of duration of mechanical ventilation or time to end of mechanical, measured as elapsed time from the start date of mechanical ventilation to the weaning date, for patients needing intubation\*
5. One-month mortality rate between the two arms\* [ Time Frame: up to 1 month ] 1-month mortality is defined as the ratio of patients who will live after 1 month from study start out of those registered at baseline
6. Change in inflammatory markers like CRP (C-reactive protein) level, d-Dimer, ferritin etc. [ Time Frame: Arm A; baseline, during treatment (Before every dose and 12 to 24 h after every dose) up to 1 month, Arm B: baseline, 12 to 24 h and approx. 7 and 14 days after randomization ]

\* Applicable for both the arm

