## **9 Efficacy Evaluation**

### **Primary Efficacy Evaluation**

Proportion of patients with deterioration of lung function as measured by Stable SpO2 without increasing FiO2 and Stable PaO2 without increasing FiO2 will be summarized using count and

percentage. The difference between two proportion with its 95% Confidence interval and associated p-values may be presented, if p-value is less than 0.05 it can be concluded that there is a statistically significant difference between two proportions.

Reduction of endo-tracheal intubation rate, measured as rate of patients needing intubation will be summarize using descriptive statistics.

Reduction in proportion of patients who need/ Non-invasive ventilation / Invasive mechanical ventilation/high flow nasal oxygen will be summarized using count & percentage.

One-month mortality rate between the two arms will be summarized. The difference between two rates with its 95% Confidence interval and associated p-values may be presented, if p-value is less than 0.05 it can be concluded that there is a statistically significant difference between two-rates.

Change in inflammatory markers like CRP (C-reactive protein) level, d-Dimer, ferritin etc will be summarize with descriptive statistics. Change from Baseline may be presented along with 95% CI.

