## **12 Key Definitions**

For few assessments (weight, physical examination, vital signs haematology, biochemistry Chest X Ray/CT scan), screening assessments will be considered as baseline assessment (as day 1).

Stable SpO2:

- Stable SpO2: Defined as absence of increase in FiO2 to maintain Spo2 ≥ 92%
- Improvement of SpO2: Defined as decrease in FiO2 to maintain SpO2 >92%

Stable PaO2:

- Stable PaO2: Defined as up to 10% change in PaO2/FiO2 ratio from baseline
- Improvement of PaO2: Defined as > 10% improvement in PaO2/FiO2 ratio from baseline (including patients weaned off oxygen)

If assessment is missing on particular day then it should be captured from assessment available in next two days.

For lab parameters, if assessment is missing on particular day, then it should be captured from assessment available in ± 2 days.

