### **13 Programming Considerations, Listing of Tables, Figures & Format, Software detail**

All tables, data listings, figures (TLFs), and statistical analyses will be generated using SAS® for Windows, Release 9.4 (SAS® Institute Inc., Cary, NC, USA) or any other validated statistical software. One SAS program will be used to create several outputs / a separate SAS program will be created for each output. Output files will be delivered in Word / pdf format.

For few assessments (weight, physical examination, vital signs haematology, biochemistry Chest X Ray/CT scan), screening assessments will be considered as baseline assessment (as day 1).

Missing data:

All attempts will be made to collect all data per protocol. Any data point that appears to be erroneous or inexplicable based on clinical judgment will be investigated as a possible outlier. If data points are identified as outliers, sensitivity analyses may be performed to examine the impact of including or excluding the outliers. Subjects who meet fatal outcome during the observing period up to 30 days will be an event. Subjects lost to follow up or withdraw consent during the observing period, will be censored at last assessment. Patient data will be censored at the time of their last observed assessment in case of lost to follow up, withdrawal consent or after 30 days of enrolment.

Following Rules may be applied for the derivation of efficacy endpoints

- Patients who discharged from hospital (with improvement, Off O2), the status at discharge will be carried forward.
- Patients who lost to follow up will be considered as Non evaluable (NE)
- Patients who worsen or met fatal outcome, status at event will be carried forward.

Note: Telephonic improvement of weaning of O2 will be considered as improved.

These rules will be applied to analyse following endpoint:

Proportion of patients with deterioration of lung function as measured by:

- Stable SpO2 without increasing FiO2
- Stable PaO2 without increasing FiO2

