## 14.2 Primary outcome measures

### 14.2.1 Primary Outcome Measures

Visit*		Arm A (N=XX)	Arm B (N=XX)
Baseline	patients with Stable SpO2 without increasing FiO2	XX (XX.X %)	XX (XX.X %)
	patients with Stable PaO2 without increasing FiO2	XX (XX.X %)	XX (XX.X %)

\*day 7, day 14, day 21 and day 30/EOS or all available visits

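### Primary endpoint 1 is named for deterioration but counted by stability, and read literally its PaO2 count drops patients who improve by more than 10%

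*SAP*

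**What the plan says.** Protocol section 5, SAP 3.2.1 and SAP 9 all call the endpoint the "Proportion of patients with deterioration of lung function as measured by" two items: stable SpO2 and stable PaO2, each without an increase in FiO2. For its analysis SAP 9 adds: "The difference between two proportion with its 95% Confidence interval and associated p-values may be presented". A p-value below 0.05 may then be read as a difference.

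SAP 12 supplies the definitions:

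- Stable SpO2: "Defined as absence of increase in" FiO2 to hold SpO2 at 92% or above. Improvement is a decrease in FiO2.
- Stable PaO2: "Defined as up to 10% change in" the P/F ratio from baseline. Improvement is a separate bullet for a gain above 10%, ending "ratio from baseline (including patients weaned off oxygen".

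Shell 14.2.1 tabulates "patients with Stable PaO2 without increasing FiO2" and the matching SpO2 row. It has no improved, deteriorated or non-evaluable row. Its footnote gives the visits as "day 7, day 14, day 21 and day 30/EOS or all available visits".

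SAP 13 lists rules that it assigns to this endpoint. Status is carried forward after discharge, worsening or death; patients lost to follow-up are non-evaluable; and "Telephonic improvement of weaning of O2 will be considered as improved". Shells 14.2.3 to 14.2.6, on types of oxygen support, count patients as stable or improved.

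**The concern.** A high value is bad by the endpoint's name and good by its measure. More importantly, the PaO2 measure as written is a band around no change. A patient who recovers and comes off oxygen falls outside it, as does one whose P/F ratio collapses. Under the SpO2 definition the recovered patient counts as a success, because a fall in FiO2 is also an absence of increase. The two components of one endpoint therefore treat the same good outcome differently.

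Two programmers working from this text could produce different numerators for the first-listed primary endpoint. The wording stable or improved appears in four neighbouring shells and not in 14.2.1, so the omission could be taken as deliberate. In an open-label trial (SAP 4.1) with periodic data review by the DSMB (SAP 11), a numerator settled late could be chosen with knowledge of the results.

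**Working it through.** The plan gives no figure for this endpoint, so there is none to reproduce. The check has three steps.

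**1. Classify patients by the written rules** (SAP 12 and shell 14.2.1).

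| Patient | Stable SpO2 row | Stable PaO2 row |
|---|---|---|
| FiO2 unchanged, P/F within 10% of baseline | counted | counted |
| FiO2 reduced, P/F up more than 10% | counted | not counted |
| Weaned off oxygen | counted | not counted |
| FiO2 increased, P/F down more than 10% | not counted | not counted |

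The PaO2 column puts recovery and worsening together; the SpO2 column does not.

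**2. Illustrate the effect on the comparison.** Assume that percent change in P/F is normal with mean m and SD 30 in each arm, and that Arm A's mean is 30 points above Arm B's. None of this comes from the documents.

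- P(stable) = Φ((10 − m)/30) − Φ((−10 − m)/30)
- P(improved) = 1 − Φ((10 − m)/30)

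For A +30: stable = 0.252 − 0.091 = 0.161; improved = 0.748; together 0.909. For B 0: stable = 0.6306 − 0.3694 = 0.261; improved = 0.369; together 0.631.

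| Mean change, A / B | Stable only, A v B | Difference (points) | Stable or improved, A v B | Difference (points) |
|---|---|---|---|---|
| +40 / +10 | 11% v 25% | −14 | 95% v 75% | +20 |
| +30 / 0 | 16% v 26% | −10 | 91% v 63% | +28 |
| +20 / −10 | 21% v 25% | −4 | 84% v 50% | +34 |
| +15 / −15 | 23% v 23% | 0 | 80% v 43% | +36 |
| +10 / −20 | 25% v 21% | +4 | 75% v 37% | +38 |
| 0 / −30 | 26% v 16% | +10 | 63% v 25% | +38 |

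Differences are rounded from unrounded values. The sign reverses in three cases, ties in one and holds in two. Under these assumptions it reverses exactly when Arm A's mean change is further from zero than Arm B's.

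Two sensitivity checks:

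- SD: at +40/+10, stable only is 6% v 34% with SD 20 and 12% v 19% with SD 40.
- Deaths counted as not stable, assumed 10% in A and 20% in B (multiply by 0.9 and 0.8): at +30/0, stable only is 15% v 21% and stable or improved is 82% v 50%.

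**3. Check with counts.** About 30 patients at 2:1 gives 20 v 10. Suppose P/F worsens by more than 10% in 2 of 20 (A) and 4 of 10 (B), and that B's other six are 4 stable and 2 improved. Stable or improved is 18/20 = 90% v 6/10 = 60% (Fisher p = 0.141), however A's 18 divide. If k of those 18 improve, the stable-only count is (18 − k)/20 against 40%:

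- k = 6: 60% v 40%, p = 0.442
- k = 10: 40% v 40%, p = 1.0
- k = 13: 25% v 40%, p = 0.431
- k = 18: 0% v 40%, p = 0.008

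With worsening held fixed, each further improver in Arm A lowers its literal count.

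**The case against.** The best reply is that pooling was intended. In SAP 12 the improvement bullet sits under the stable PaO2 heading. SAP 13 writes its rules for this endpoint alone, and classing telephone-reported weaning as improved would serve little purpose if improved patients failed. This is probably right, but it is inference. Shell 14.2.1 supports higher as better, yet the endpoint's name says the opposite.

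A reader might go further in four ways that the documents do not support:

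- **That the endpoint has no denominator.** SAP 6 bases percentages on non-missing values, and SAP 13 makes patients lost to follow-up non-evaluable. What is missing is a row to show them.
- **That a patient whose P/F rises on a higher FiO2 has no class.** Take PaO2 60 on FiO2 0.4 (60/0.4 = 150) moving to 100 on 0.5 (100/0.5 = 200). The gain is 50/150 = 33%, which SAP 12 calls improved. The conflict is only with the endpoint's label.
- **That P/F in Arm B stops at about Day 14.** That time frame belongs to secondary endpoint 3. Protocol 8.1 schedules P/F weekly to Day 22 without limiting it to one arm.
- **That the trial's result will be reversed.** The reversal depends on assumed means and SD. Mean P/F is also tabulated by arm (shell 14.1.7, Table S2), so a reversal would be noticed.

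It also stands that p-values are optional, that shell 14.2.1 has no p-value row, and that about 30 patients were planned without a formal calculation.

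**Conclusion.** The point holds, and should be fixed. The endpoint's name contradicts its measure, and the written PaO2 rule with shell 14.2.1 leaves improvers out of the numerator. This can be read directly from the documents and needs no assumption. It affects the PaO2 component only.

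The size is illustrative. Under the normal model with SD 30% and a 30-point benefit, the literal count gives differences from −14 to +10 points, where stable or improved gives +20 to +38. Whether the difference reverses or is only muted depends on where the two arm means lie, which the documents do not say.

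**What to change.** **SAP 3.2.1, 9 and 12.** State endpoint 1 as the proportion stable or improved (without deterioration), higher favourable, reported separately for SpO2 and PaO2. For PaO2 keep the SAP's thresholds: a fall in P/F of no more than 10%, or a gain above 10%, or weaned off oxygen; death counts as not stable. Classify PaO2 on P/F, as SAP 12 is written, and reconcile the label about not increasing FiO2 with that.

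**Shell 14.2.1.** Add improved and deteriorated rows for each component (four rows) and a non-evaluable row. Take percentages among evaluable patients, in line with SAP 6 and 13. For example, with 7 stable or improved, 2 deteriorated and 1 non-evaluable, deteriorated is 2/9 = 22%, not 3/10 = 30%. Name one visit for any p-value on this endpoint.

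**Timing and route.** Make the SAP change before any between-arm data are reviewed, and in any case before database lock, the limit that SAP 1 sets for revisions. SAP 1 does not cover the protocol, so Protocol section 5 needs an amendment or a clarification.

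**Cost.** Wording in two documents and five shell rows; no new data.

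**Separate and minor.** Endpoint 5 defines one-month mortality by patients who survive, while SAP 13 and shell 14.2.7 count deaths. Align the wording with deaths.

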Source data is all information, original records of clinical findings, observations, or other activities in a clinical study necessary for the reconstruction and evaluation of the study. Source data are contained in source documents. Examples of these original documents, and data records include: hospital records, clinical and office charts, laboratory notes, memoranda, subject's diaries or evaluation checklists, pharmacy dispensing records, recorded data from automated instruments, copies or transcriptions certified after verification as being accurate and complete, microfiches, photographic negatives, microfilm or magnetic media, x-rays, subject files, and records kept at the pharmacy, at the laboratories, and at medico-technical departments involved in the clinical study.

Location of Data

All records and documents pertaining to the study will be maintained in the permanent files of the Investigator and will be available for inspection by the authorized party at any time.

Statistical Analysis

In general, continuous variables is summarized using descriptive statistics such as mean, standard deviation, 95% confidence interval (CI), minimum, and maximum. Categorical variables are summarized using proportions (counts and percentages). All statistical tests will be performed at 5% level of significance (two-sided test) and p-value<0.05 considered statistically significant (if necessary). All statistical analysis will be performed using SAS® (version 9.4 or higher) system software (SAS Institute Inc., USA)/or R/or EAST/or NCSS software.

11.Administrative Procedures

Ethics and Good Clinical Practice

This research will be carried out in accordance with the clinical research guidelines established by the basic principles defined in the revised New Drugs and Clinical Trials 2019, India and the principles enunciated in the Declaration of Helsinki [Ethical Principles for Medical Research Involving Human Subjects, revised, October 2013]. The investigator is responsible for overall activities at the center in accordance with Indian ICH-GCP guidelines, current New Drugs and Clinical Trials 2019 and ethical guidelines for biomedical research on human subjects issued by ICMR.

Interim study report - Data will be provided to DSMB (constituted prior to first patient screened) on a periodic basis. Based on DSMB recommendation, interim clinical study report may be prepared and submitted to DCGI/regulatory agencies.

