### 3.2.2 Secondary endpoints

1. Biomarkers (IL-6, TNF-a, IL1, IL17, etc...) [ Time Frame: Arm A; baseline, during treatment (Before every dose and 12 to 24 h post dose) up to 1 month, Arm B; baseline, 12 to 24 h and approx. 7 and 14 days after randomization ]
2. Lymphocyte count [ Time Frame: Arm A; baseline and before every dose up to 1 month, Arm B; baseline, approx. 7 and 14 days after randomization ] Lymphocyte count assessed by routinely used determination of blood count
3. PaO2 (partial pressure of oxygen) / FiO2 (fraction of inspired oxygen, FiO2) ratio (or P/F ratio) [ Time Frame: Arm A; baseline, during treatment (Before every dose and 48 h post dose) up to 1 month, Arm B: baseline, 48 h and approx. 7 and 14 days after randomization] calculated from arterial blood gas analyses (values from 300 to 100)
4. Number of participants with treatment-related side effects as assessed by Common Terminology Criteria for Adverse Event (CTCAE) version 5.0 [ Time Frame: during treatment and up to 30 days after the last treatment dose ]\* graded according to CTCAE criteria (v5.0)
5. Radiological response [ Time Frame: at baseline, after seven days and if clinically indicated (up to 1 month) ]\* Thoracic CT scan or Chest XR
6. Duration of hospitalization [ Time Frame: from baseline up to patient's discharge (up to 1 month) ]\* Days of hospitalization and ICU

7. Remission of respiratory symptoms [ Time Frame: up to 1 month ]\* time to independence from non-invasive mechanical ventilation calculated in days
8. Remission of respiratory symptoms [ Time Frame: up to 1 month ]\* time to independence from oxygen therapy in days

\* Applicable for both arms

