### **4.4 Exclusion Criteria**

1. Known severe allergic reactions to monoclonal antibodies
2. Active tuberculosis (TB) infection
3. History of inadequately treated tuberculosis or latent tuberculosis

Note: Latent tuberculosis should be excluded based on history, physical examination and chest x ray before dosing (day 1). QuantiFERON TB also should be performed, however considering criticality of patient condition, patient can be dosed without QuantiFERON TB test results. If

QuantiFERON TB test is positive, then continuation of patient in the study is investigator's discretion considering benefit-risk evaluation with the sponsor.

4. In the opinion of the investigator, progression to death is highly probable, irrespective of the provision of treatments
5. Patient on invasive mechanical ventilator support.
6. Have received oral anti-rejection or immune-suppressive drugs within the past 6 months  
Note: Patient receiving oral anti-rejection or immune-suppressive drugs regularly in the last 6 months will be excluded. Patient will be included if received short course of steroids.
7. Participating in other drug clinical trials like using anti-IL-6 therapy like tocilizumab (participation in COVID-19 anti-viral trials may be permitted if approved by Sponsor)
8. Patient on treatment of anti-IL-6 or plasma therapy as a part of supportive care
9. Pregnant or breastfeeding, or positive pregnancy test in a pre-dose examination
10. Any serious medical condition or abnormality of clinical laboratory tests that, in the investigator's judgment, precludes the patient's safe participation in and completion of the study
11. Patients with known history of Hepatitis B, Hepatitis C or HIV
12. Absolute Neutrophils count (ANC) <1000 / mm^3
13. Platelet count <50,000 / mm^3
14. Absolute Lymphocyte count (ALC): <500/mm^3

Note: ANC, ALC and platelet counts can be done in local lab in the hospital.

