## **6 General Aspects for Statistical Methods**

In general, metric variables and derived parameters will be presented using descriptive summary statistics including arithmetic mean, standard deviation, median, minimum and maximum.

Categorical variables will be presented using descriptive summary statistics including number of patients and percentages. Percentages of patients will be based on non-missing values. The presentation will be by treatment group. Individual values as well as minimum and maximum will be presented with the same number of decimal places as the raw data. Derived parameter will have as many decimal places as the measured number with the smallest number of decimal places. Descriptive statistics, such as arithmetic/geometric mean and median will be presented with an additional decimal place and standard deviation with two additional decimal places as the raw or derived data. All relevant subject data will be included in the listings; and all subjects entered into the database will be included in subject data listings. SAS 9.4 or any other validated software will be used for analysis purpose and generating Tables, Listings & Figures. P-values less than 0.05 may be reported as statistically significant.

The formatting of the final version of a table, figure, or listing may differ from what is presented in the mock shell or the presentation of the results may be changed, however the key content will remain unchanged. Additional tables, figures, and listings may be generated to supplement the planned output.

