## Listing of Tables, Figures & Format

Table, figure, and listing shells are presented in Appendices 14. The formatting of the final version of a table, figure, or listing may differ from what is presented in the shell or the presentation of the results may be changed, however the key content will remain unchanged. Additional summaries/data points may be included in the final version of a table, figure, or listing, as well. Additional tables, figures, and listings may be generated to supplement the planned output.

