### Listing 16.1.12 Study Treatment - Supportive Care/Oxygen Therapy

Treatment Group	Subject ID	Name of treatment	Start date of Dose	End date of Dose	Dose	Frequency	Route	Start Time of infusion	Was infusion interrupted	Reason for infusion interruption	Stop time of infusion interruption	Restart Time of infusion	Delivery mode for inhalation	Date of intubation	Start Time of intubation	Date of extubation	Start Time of extubation	Was weaning from mechanical ventilation done?	Date of weaning	Time of weaning	Reason for change	
												S										
XXXXXX	XXX	XXX	XXX	XXX	XXX	XXX	XXX	XXX	XX	XX	XXX	XX	XX	X	XX	X	XX	XXXX	X	X	X	
XXXXXX	XXX	XXX	XXX	XXX	XXX	XXX	XXX	XX	XX	XX	XX	XX	XX	X	XX	X	XX	XXXX	X	X	X	

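### Primary endpoint 4 (ventilation time) has no analysis of its own, and no duration endpoint has a stated rule for patients who die

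*SAP*

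**What the plan says.** **Endpoint 4.** SAP 3.2.1 (and Protocol section 5) lists ventilation time as the fourth of six primary endpoints, "measured as elapsed time from the start date of mechanical ventilation to the weaning date, for patients needing intubation". SAP 4.4 excludes any "Patient on invasive mechanical ventilator support", so everyone who contributes a value was intubated after entry.

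**Its analysis.** In SAP 9 the text for endpoint 3 reads "Reduction in proportion of patients who need/ Non-invasive ventilation / Invasive mechanical ventilation/high flow nasal oxygen will be summarized using count & percentage". The next sentence is about mortality; endpoint 4 is skipped. No shell in SAP 14.2 covers it and SAP 14.1.11 has no row for it. Among the planned outputs, weaning appears only in Listing 16.1.12 ("Was weaning from mechanical ventilation done"). What could apply by default is generic: SAP 6 ("metric variables and derived parameters will be presented using descriptive summary statistics including arithmetic mean, standard deviation, median, minimum and maximum"), the Protocol's Statistical Analysis paragraph ("continuous variables is summarized using descriptive statistics such as mean, standard deviation, 95% confidence interval (CI), minimum, and maximum"), and the option in SAP 13 that "Additional tables, figures, and listings may be generated to supplement the planned output".

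**The other durations.** Hospitalisation is measured "from baseline up to patient's discharge (up to 1 month"). SAP 9 and SAP 14.1.11 summarise hospital days, ICU days and time to NIV or oxygen independence by N, mean, median and range.

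**Death.** SAP 13 makes three relevant statements:
- A death within 30 days counts as an event. No endpoint is named.
- Loss to follow-up, withdrawal and reaching 30 days lead to censoring. Death is not in that list.
- Status at death is carried forward, but only for the stable SpO2/PaO2 endpoint.

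Figure 4 is a Kaplan-Meier plot for time-to-event endpoints, none of them named.

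**The concern.** Death precludes weaning, discharge and oxygen independence. A summary of time to any of these must say what a death contributes, and here there are at least four possibilities:
- the patient is dropped;
- the duration stops at death;
- the patient is censored at death;
- the death counts as the event.

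The documents choose none of them, although each gives a different picture. Dropping deaths compares subsets that randomisation did not create. Stopping at death shortens the stay in an arm with many early deaths. Censoring estimates recovery as if nobody could die. Counting death as the event credits a death as reaching the favourable outcome.

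The trial is open label, so this choice should be on paper before the data are seen by arm. For a primary endpoint, the analysis itself should be on paper too.

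**Working it through.** There is no plan figure to reproduce: the documents give no mortality, intubation, weaning or death-timing rates and no formal sample size. Every rate below is an assumption. Recovery is identical in both arms, so any difference comes from the handling of death. The first figure is the arm with fewer deaths.

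**1. Hospital stay.** Assumed: time off oxygen lognormal, median 10 days, sigma 0.5; discharge 3 days later; cut at Day 30; deaths uniform on days 2 to 12 (mean day 7); nobody who dies comes off oxygen or is discharged first. Mean stay without death is 14.19 days.

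- Deaths dropped: 14.2 v 14.2 at any mortality.
- Stay ended at death: (1 − m) × 14.19 + m × 7.

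| Mortality m | Stay ended at death |
|---|---|
| 5% v 20% | 13.83 v 12.75 |
| 10% v 30% | 13.47 v 12.03 |
| 20% v 40% | 12.75 v 11.31 |

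The sign depends on timing. With deaths on days 10 to 28 (mean 19) at 10% v 30%, it reverses: 0.9 × 14.19 + 0.1 × 19 = 14.67 v 0.7 × 14.19 + 0.3 × 19 = 15.63. If patients may be discharged before dying, it does not reverse (14.1 v 13.8).

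**2. Off oxygen by Day 30 (a candidate for Figure 4).** Same inputs, 10% v 30%. Without death, the probability is F(30) = Φ(ln 3 / 0.5) = 0.986.

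- Death competing: (1 − m) × 0.986 = 88.7% v 69.0%.
- Death counted as the event: (1 − m) × 0.986 + m = 98.7% v 99.0%.
- Death censored: 1 − exp{−∫ (1 − m) f(t) / [(1 − m) S(t) + m G(t)] dt} over 0 to 30, where f and S are the density and survivor function of time off oxygen and G that of time to death. Result: 98.5% v 98.3%.

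If patients can come off oxygen before dying, death competing gives about 91% v 77% and death censored 98.6% in both arms. With deaths on days 10 to 28 and nobody off oxygen first, the censored curve hides less: 95.9% v 86.8%, still against 88.7% v 69.0%.

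**3. Endpoint 4.** Assumed: ventilation starts uniformly on days 1 to 10; time to weaning lognormal, median 8 days, sigma 0.5; 30% v 70% of intubated patients die. About 0.985 would be weaned by Day 30 without death.

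| Ordering assumed | Mean days, weaned patients | Intubated patients with a value |
|---|---|---|
| Nobody who dies is weaned first | 8.8 v 8.8 | 0.7 × 0.985 = 69% v 0.3 × 0.985 = 30% |
| May be weaned first; deaths 1 to 10 days after intubation | 8.4 v 7.5 | 77% v 48% |
| Same; 1 to 14 days | 8.4 v 7.6 | 82% v 59% |
| Same; 2 to 20 days | 8.5 v 7.9 | 87% v 73% |

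The summary either hides the difference in deaths or makes the arm with more deaths look quicker to wean.

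**4. How few values.** About 30 patients at 2:1 is roughly 20 v 10. With 20% intubated (assumed) and the first row above, expected values are 20 × 0.2 × 0.69 = 2.8 in Arm A and 10 × 0.2 × 0.30 = 0.6 in Arm B. Arm B has none with probability (1 − 0.06)^10 = 0.54.

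**5. Cross-check with constant hazards.** Take weaning at 0.05 per day, death at d per day and a 30-day horizon. P(weaned) = 0.05/(0.05 + d) × [1 − exp(−30(0.05 + d))]. The Kaplan-Meier median is ln 2/0.05 with death censored and ln 2/(0.05 + d) with death as the event. As d goes from 0 to 0.10, P(weaned) falls from 0.78 to 0.33. The censored median stays at 13.9 days, the event median falls from 13.9 to 4.6, and the mean among weaned patients falls from 11.4 to 6.3.

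**The case against.** The plan is not silent on death. Mortality has its own difference, confidence interval and p-value (SAP 14.2.7). Deaths also appear in disposition (14.1.2), survival status (14.2.9) and an overall summary by arm (SAP 9). SAP 14.1.10 tabulates discharge during the study, so the count without discharge can be seen next to the stay table, and 14.1.11 prints N. No test is planned on any duration, and the study is described as exploratory in size. This stands and limits the harm. It does not close the gap: none of these outputs says which patients lack a given duration because they died, or what a death contributes to that row.

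The SAP 13 event sentence could be offered as the missing rule. It reads most naturally as mortality. Applied to weaning or oxygen independence, it would turn a death into a success, and it cannot act on the mean and median shells, which carry no event status.

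A reader might also infer more than the documents support:
- *Endpoint 4 cannot be analysed.* It can, by the generic descriptive default; what is missing is a specific analysis and a death rule.
- *The default covers survivors only.* It covers weaned patients, including any who die after weaning.
- *The SAP instructs that deaths be censored or counted as recovery.* It does neither; it leaves both open.
- *The arm with more deaths will look better.* That depends on when deaths occur, as steps 1 and 3 show.
- *A between-arm comparison of free days is required.* It is not. It would largely repeat the mortality comparison and be imprecise at this size.

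**Conclusion.** The concern holds. A listed primary endpoint has no analysis text and no table. Its default summary would rest on weaned patients only, perhaps a handful. Hospital, ICU, NIV and oxygen durations have no stated treatment of death, and the scope of the SAP 13 event sentence and of Figure 4 is undefined.

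Under the assumed inputs, the unstated rule moves mean stay between no difference and about 1.4 days in favour of the arm with more deaths. It also turns a gap of about 20 percentage points in oxygen independence by Day 30 into almost none. These figures show the mechanism. They are not forecasts for this trial, and they change with mortality, death timing and whether patients recover before dying.

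This should be corrected. It does not undermine the mortality analysis, which is separate. The endpoint 4 gap is the weightier part; the other durations are secondary and descriptive.

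**What to change.** SAP section 1 allows revisions before database lock. In that revision:

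1. Add an endpoint 4 row or table, keeping the protocol definition. State how death enters each duration (ventilation, hospital, ICU, NIV, oxygen). Beside each row, print the number of deaths and the number of patients without a value.
2. Limit the SAP 13 event sentence to mortality and name the endpoints in Figure 4. Show weaning, discharge and oxygen independence as cumulative incidence with death as a competing event.
3. Optionally, as a descriptive supplement by arm, report ventilator-free days to Day 30 with death set to 0.

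The cost is a few derived variables and displays. The dates needed are largely in Listings 16.1.12 (intubation, extubation, weaning), 16.1.16 (admission, discharge, ICU) and 16.1.17 (death). The downsides are modest: cumulative incidence curves with about 10 patients in Arm B will be coarse, and free days mix mortality with duration, overlap with primary endpoint 5 and are imprecise with about 30 patients. If item 3 is used, the revision should also state what is assumed between early discharge and the Day 30 telephone contact in Protocol 8.1.
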